9.5.3. Adverse Events

Adverse events will be collected once subjects meet all the study eligibility criteria and are randomized and administered study drug. However, all adverse event summaries will be restricted to Treatment-Emergent Adverse Events (TEAE), which are defined as those AEs that occurred after first dosing and those pre-existing conditions that worsened during the study. If the start time for an AE that occurs on the first date of dosing is unknown, then the event will be assumed to be a TEAE. If the start date of an AE is unknown, the event will be assumed to be a TEAE.

The number of subjects experiencing a particular event, the percentage of subjects experiencing the event, and the total number of events will be presented. The following summaries will be created:

- Overall summary of TEAEs, which includes the subject incidence of TEAEs and total number of unique TEAEs from each of the following AE summaries without regard to MedDRA system organ class or preferred term
- TEAE by SOC and preferred term
- TEAE by SOC and preferred term by injection number. Subjects and events are attributed to a given injection only if the event start date (subject to the missing date and

time imputation rules of Section 8.6.3) occurs on or after the date and time of that injection and not before the next injection.

- TEAE by SOC, preferred term and protocol version
- TEAE by SOC, preferred term and maximum severity. At the across-SOC and preferred term levels of subject summarization, a subject is classified according to the highest severity if the subject reported one or more events; severity within an SOC is not summarized. AEs with missing severity will be considered severe for this summary.
- TEAE by SOC, preferred term and closest relationship to study treatment (Related/Not Related). At each level of subject summarization, a subject is classified according to the closest relationship if the subject reported one or more events. AEs with a missing relationship will be considered 'related' for this summary; events classified as 'possibly', 'probably' or 'definitely' will be considered 'related'.

A listing of treatment-emergent SAEs (if any) will be provided, and if more than one occurs within any given preferred term, a summary of treatment-emergent SAEs by SOC and preferred term will be created.

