The number of copies of VM202 in whole blood will be determined at Day 0 (pre-injection, and 2 hours $[\pm 1 \text{ hour}]$ post injection), at Day 14 (pre-injection, and 2 hours $[\pm 1 \text{ hour}]$ post injection), at Day 28 (pre-injection, and 2 hours $[\pm 1 \text{ hour}]$ post injection), at Day 42 (pre-injection, and 2 hours $[\pm 1 \text{ hour}]$ post injection) at Day 60 and at Day 90.

Measurement of target ulcer will be performed at each follow-up visit until complete wound closure is achieved or until study exit. ABI, TBI, and the Cardiff Wound Impact Questionnaire (CWIQ) will be conducted on Day 0, Day 120, and Day 210 Visits. TcPO₂ will be assessed as a substudy at 3 -10 sites on Day 0, Day 120, and Day 210 Visits. Adverse events will be recorded after first study drug administration and throughout the 7-month follow-up period.

SCHEDULE OF EXAMINATIONS

Screening (Day -45 to Day -7)

Day 0

Day 14 ± 3 days

Day 28 ± 3 days

Day 42 ± 3 days Day 60 ± 3 days Day 74 ± 3 days Day 90 ± 7 days Day 120 ± 7 days Day 210 ± 14 days

STUDY ENDPOINTS

The primary study endpoint is the proportion of subjects with a target wound closure by the 4-month follow-up. Complete wound closure is defined as skin re-epithelization without drainage or dressing (primary endpoint), confirmed at a second scheduled or unscheduled visit two weeks $(14 \pm 5 \text{ days})$ later (secondary endpoint). Active and placebo arms will be compared to determine treatment effect.

Other endpoints will include:

- Time to complete healing of foot ulceration in each group
- Percent change in wound size
- Formation of new ulcers on the target foot
- Change in CWIQ
- Major amputations
- Minor amputations
- Change in ABI
- Change in TBI
- Change in TcPO₂ at select sites only

TABLE OF CONTENTS

INVE	STIGATOF	r's Agre	EEMENT	3
STUD	Y SYNOP	SIS		4
TABL	LE OF CON	NTENTS		10
ABBI	REVIATIO	NS		14
PERS	ONNEL A	ND FACII	LITIES	16
1.	BACKGR	OUND		20
	1.1.		aling Foot Ulcers	
			PAD and Diabetes – Two Roads to a Chronic Wound	
	1.2.		Healing	
	1.3.	Current	Treatment Options	22
	1.4.	Unmet	Medical Need	22
	1.5.		cyte Growth Factor (HGF) and Wound Healing	
	1.6.	VM202	2 for the Treatment of Chronic Foot Ulcers	
		1.6.1.	J	
		1.6.2.	VM202 Wound Healing Data - Rationale	
		1.6.3.	Phase I Study of VM202 in Patients with Critical Limb Ischemia	
		1.6.4.	Phase II Study of VM202 in Patients with Critical Limb Ischemia	
		1.6.5.	Clinical Experience Conclusions	
	1.7.	Study a	and Dose Rationale	28

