5.3. REPORTING/RECORDING OF AES

Throughout the course of the study, all efforts will be made by the investigator to remain alert to possible AEs. The first concern will be the safety of the subject, and for providing appropriate medical intervention. The period of observation for collection of AEs occurs following the first study drug administration until the 7-month follow-up visit. Any AE should be recorded in the EDC. Any events occurring before the injections will be added to the medical history.

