3. STUDY DESIGN

This is a phase III, randomized, double-blind, placebo-controlled, multicenter, 7-month study designed to assess the safety and efficacy of intramuscular injections of VM202 in the calf of diabetic patients with chronic nonhealing foot ulcers and concomitant PAD. Subjects with confirmed PAD and diabetes aged \geq 18 years to \leq 80 years diagnosed with nonhealing foot ulcers will be screened for study eligibility after giving informed consent.

At Screening, standard of care will be initiated that will continue for the duration of the study, as follows:

- Surgical debridement of necrotic tissue or devitalized tissue
- Use of appropriate off-loading when ambulating
- Maintenance of moist wound environment

Three hundred patients (from up to 30 study centers) who meet the eligibility criteria will be randomized in a 2:1 ratio to one of two treatment groups: 200 patients with VM202 (16 mg) plus standard of care or 100 subjects with placebo plus standard of care, respectively. Safety will be monitored throughout the study by an independent Data Safety Monitoring Board (DSMB, Section 8.5).

Patients will receive intramuscular injections in the ipsilateral calf of the affected foot with the target ulcer of either VM202 or placebo on Day 0, Day 14, Day 28, and Day 42 as follows:

Treatment: Days 0, 14, 28, and 42

TREATMENT]	DOSE VM20	FINAL DOSE		
GROUP	DAY 0	DAY 14	DAY 28	DAY 42	VM202 (mg)
VM202	4	4	4	4	16
Placebo	0	0	0	0	0

0 indicates injections of Placebo

VM202 will be delivered in a solution of 0.5 mg VM202 / mL. All subjects will receive sixteen (16) 0.5-mL intramuscular injections of VM202 or placebo at each injection visit.

The schedule of study visits and the clinical parameters that will be measured at the visits are summarized in Table 1 to Table 3 below.

The subjects' target ulcer will be evaluated by photograph, surface area, depth, perimeter and volume measurements. Subjects must have a non-healing ulcer on Day 0 that meets study entry inclusion criterion # 5 and does not meet exclusion criterion #6 to be eligible for study participation. Subjects will continue to come to the clinic once a week for dressing changes and wound assessment until the ulcer has healed or study exit, whichever comes first. Measurement of the target ulcer will be performed at each follow-up visit until complete wound closure or study exit.

Further details on the study procedures and conduct are provided in the protocol.

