4.2. Other Efficacy Endpoints

- Time to complete wound closure of foot ulcer
- Proportion of subjects with a target wound closure by 7 months
- Percent change in wound volume at 2 months (Day 60), 2.5 months (Day 74), 3 months (Day 90), 4 months (Day 120), and 7 months (Day 210)
- Percent change in wound perimeter, area and wound depth at 2 months, 2.5 months, 3 months, 4 months, and 7 months
- Proportion of subjects with formation of new ulcers on the target foot by 2 months, 2.5 months, 3 months, 4 months, and 7 months
- Time to major amputation in the target limb
- Time to minor amputation in the target limb
- Change in target limb ABI at 4 months and 7 months
- Change in target limb TBI at 4 months and 7 months
- Change in TcPO₂ at 4 months and 7 months
- Change in the overall quality of life and each domain score (well-being, physical symptoms and daily living, social life) of CWIQ from Day 0 at 4 months and 7 months

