8.2. Visit Windows

Data at each scheduled follow-up visit will be analyzed according to the nominal visit identified on the data record. In case of multiple different visits identified with the same nominal visit, the visit with the visit date closest to the target days of each protocol-specified visit schedule (Table 5) will be used for the efficacy analyses of exploratory endpoints assessed at specific months. For visits with the same distance to the target days, the later nominal visit record will be used. Data from the other visits (if any) will be provided in data listings.

Table 5 Target Day and Month Descriptor

	1 st INJECTION	2 ND INJECTION	3 RD INJECTION	4 TH INJECTION	DAY 60	DAY 74	DAY 90	DAY 120	DAY 210
TARGET DAY	0	14	28	42	60	74	90	120	210
FOLLOW-UP MONTH	-	-	-	-	2	2.5	3	4	7

Data from 'weekly wound assessment and dressing change', 'confirmation of ulcer healing', 'early withdrawal', and any unscheduled study visits will be used in addition to the scheduled target day visits to determine efficacy endpoints that are the response rate by a given follow-up visit (e.g., the primary efficacy endpoint) or a time to event endpoint (e.g., time to complete wound closure).

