8.6.3. Missing Dates and Times

If a start or stop date for an adverse event or a concomitant medication is completely missing, it will not be imputed. If that date is partially missing, imputed dates specified in Table 6 will be used to derive the duration of the adverse event or the duration of the medication use. If the start or stop date for an adverse event is not missing but the corresponding time is partially or completely missing, imputed times specified in Table 7 will be used to derive the duration of the adverse event. For adverse event attribution relative to a specific injection, a missing start date and time should default to the date and time of the immediately documented prior injection. Missing years will not be estimated under any conditions.

Table 6 Imputation Rules for Partial Adverse Event or Concomitant Medication Start and Stop Dates

	Missing	IMPUTATION	EXCEPTION
Start Date	Day	01	Default to Study Day 0 (day of first injection procedure) if an event starts in the same year and month as Study Day 0
	Day/Month	01JAN	Default to Study Day 0 if an event starts in the same year as Day 0
Stop Date	Day/Month	Last day of the month	Default to the End of Study Date if the imputed event stop date is after the End of Study Date or before start day of the event
	Day/Month	31DEC	Study Date or before start day of the event

Table 7 Imputation Rules for Partial or Missing Adverse Event Start and Stop Times

	Missing	IMPUTATION	EXCEPTION
Start Time	Minute	00	Default to time of first injection if an event
	Hour: Minute	00:00	starts on Study Day 0
Stop Time	Minute	59	(none)
	Hour: Minute	23:59	Default to 23:59 on the End of Study Date if
			the imputed event stop date is after the End
			of Study Date or before start day of the event

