9.5.2. Injection Site Adverse Events

The number and percentage of subjects with an injection site AE, by type (injection site reaction, ulceration, allergic reaction/hypersensitivity) and overall, will be summarized by treatment group at each weekly 'wound assessment and dressing change' visit and for the preand post-injection assessments on scheduled injection visit days (i.e., Days 0, 14, 28, and 42). The denominator for these percentages will be based on the number in the risk set following a given injection, which is the number of subjects who received that specific injection. The number and percentage of subjects for each grade within a given type of injection site AE will be summarized by treatment group at each assessment time point.

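### The TEAE-by-injection rule in SAP 9.5.3 is reversed as worded and, as intended, leaves the last injection's window open, which distorts comparison of injections within an arm

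*SAP*

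**What the plan says.** - **Attribution rule (SAP 9.5.3).** In the table by SOC, preferred term and injection number, an event counts for an injection only if its start date "occurs on or after the date and time of that injection and not before the next injection". The section presents numbers and percentages of subjects and numbers of events. For this table it gives no end to the window after the last injection, no person-time and no denominator.
- **Missing starts (SAP 8.6.3).** For attribution to an injection, "a missing start date and time should default to the date and time of the immediately documented prior injection".
- **Schedule (SAP 3).** Subjects receive "either VM202 or placebo on Day 0, Day 14, Day 28, and Day 42".
- **AE collection (Protocol 5.3).** "The period of observation for collection of AEs occurs following the first study drug administration until the 7-month follow-up visit". SAP 4.2 equates 7 months with Day 210. The protocol synopsis gives that visit as "Day 210 ± 14 days" and allows 3 days either side for injections 2 to 4.
- **Neighbouring table (SAP 9.5.2).** For injection site AEs the denominator is the risk set, "which is the number of subjects who received that specific injection".
- **Context.** Safety results are descriptive, untested and shown by actual treatment (SAP 9.5). The study stopped early (SAP 10).

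**The concern.** There are two separate faults in one sentence.

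First, in ordinary English an event that is not before the next injection is one that starts at or after it. The rule therefore asks for the opposite of what an attribution window needs. A programmer who follows the text produces a wrong table. One who guesses the intent produces a reasonable table, but one that the SAP does not specify.

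Secondly, the natural repair leaves the last window without an end. What this table adds to the plain SOC and preferred-term table is the split by injection. If one column covers many times the observation period of the others, counts and percentages in that column rise for that reason alone. SAP 5.3.2 identifies new foot ulcers and amputations from AE data, so events of that kind starting months after Day 42 would be listed under injection 4 alongside any early reaction to it.

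**Working it through.** The plan gives no window length, AE rate or other figure for this table, so there is nothing to reproduce. The check is date arithmetic on the plan's own schedule.

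**1. The rule applied to example events** (injections on Days 0, 14, 28, 42)

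| Event starts | Literal rule credits | Intended rule credits |
|---|---|---|
| Day 5 | none | injection 1 |
| Day 20 | injection 1 | injection 2 |
| Day 35 | injections 1 and 2 | injection 3 |
| Day 100 | injections 1, 2 and 3 (and 4, if the absence of a next injection is ignored) | injection 4 |

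Under SAP 8.6.3 an event with a missing start goes to the injection before it. Only the intended column agrees with that.

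**2. Window lengths under the intended rule**

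- Injections 1 to 3: 14 − 0 = 14, 28 − 14 = 14, 42 − 28 = 14 days.
- Injection 4: 210 − 42 = 168 days.
- Ratio: 168/14 = 12. Share of the 210 days: 168/210 = 80% for injection 4, against 14/210 = 6.7% for each of the others.

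With the permitted visit windows:

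- Injection 1: 14 ± 3, or 11 to 17 days.
- Injections 2 and 3: 25 − 17 = 8 to 31 − 11 = 20 days for injection 2, and the same for injection 3.
- Injection 4: 196 − 45 = 151 to 224 − 39 = 185 days.

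The 12-fold ratio is therefore nominal. A subject who stops after injection 1, 2 or 3 has the open window at that injection instead.

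**3. Shorter follow-up.** The documents do not say how far the early stop cut follow-up. As examples:

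- Ending at Day 120: 120 − 42 = 78 days, 78/14 = 5.6 times the others.
- Ending at Day 90: 90 − 42 = 48 days, 48/14 = 3.4 times the others.

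**4. Effect on the table at a constant event rate.** Assume all four injections, full follow-up and no effect of dose order. Expected events are rate × days/365.25, so injection 4 has 12 times the events of each other injection at any rate. The proportion of subjects with at least one event is 1 − exp(−rate × days/365.25). This depends on the rate, which the documents do not give, so a range is shown:

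| Assumed events per subject-year | Injections 1, 2, 3 (14 days each) | Injection 4 (168 days) |
|---|---|---|
| 0.25 | 1.0% | 10.9% |
| 1 | 3.8% | 36.9% |
| 4 | 14.2% | 84.1% |

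For example, at 1 per year: 1 − exp(−14/365.25) = 3.8% and 1 − exp(−168/365.25) = 36.9%. The same pattern arises in both arms.

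**The case against.** The best defence of the wording is that SAP 8.6.3, which 9.5.3 itself invokes, fixes the intent, so nobody is likely to program the literal rule. That is probably true, but it does not make the sentence correct. The two sections disagree and the rule has to be reworded.

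The best defence of the open window is the placebo arm. A reader might infer that the table would falsely show VM202 toxicity rising with the fourth dose. The documents do not support that. Placebo subjects are injected on the same days, so their last window is equally open and both arms would rise together at injection 4. Protocol 6.3.3 evaluates safety against control, and SAP 9.5 plans no tests. If follow-up is similar in the arms, window length does not bias the VM202-placebo contrast within an injection. This part of the objection stands, and it limits the point to comparisons across injections within an arm.

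Three further limits also stand:

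- Neither document states what the table is for, and local tolerability by injection is already covered in SAP 9.5.2.
- SAP 1 lists 7 + 5 + 16 + 16 = 44 enrolled subjects (about 29 and 15 if 2:1 held). Cells by SOC, preferred term and injection will be small and the practical consequence modest. Equally, a placebo group of that size is a weak visual check on a within-arm rise.
- The missing denominator is silence rather than conflict, since 9.5.3 states none for this table.

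**Conclusion.** The point holds in two parts. The rule as written is reversed and inconsistent with SAP 8.6.3; this rests on no assumption. As intended, it gives nominal windows of 14, 14, 14 and 168 days, with no closing date, person-time adjustment or stated denominator to offset the difference.

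At a constant rate with full follow-up, injection 4 would show 12 times the events of each earlier injection and 80% of the total. The ratio falls to about 5.6 or 3.4 if follow-up ended at Day 120 or Day 90. The corresponding subject percentages depend on an assumed rate and should be read only as the range shown.

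The consequence is that the table could mislead when injections are compared within an arm. It is not evidence of bias between VM202 and placebo, and it does not touch the primary analysis.

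**What to change.** In SAP 9.5.3:

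1. Reword the rule so that an event belongs to an injection if it starts at or after that injection's date and time and earlier than the next injection's.
2. For the last injection a subject received, whichever it was, close the window 14 days later, to match the nominal spacing of the others. On the full schedule this gives 14, 14, 14 and 14 days. Alternatively, report events per person-time, which also absorbs the 8 to 20 day variation in actual spacing.
3. Show later events in a separate post-treatment follow-up column. On the full schedule that column covers Days 56 to 210, which is 210 − 56 = 154 days.
4. Use as denominator the subjects who received that injection, as SAP 9.5.2 already does.

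The cost is a few sentences and one extra column, with no new data. The 14-day cut-off is a convention and should be described as one.

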6.3.3. SAFETY

Safety analyses in this study will evaluate the safety profile of VM202, as compared with control. No formal statistical testing will be conducted for the safety analyses. All subjects in the safety subset will be included in these analyses. Subjects will be grouped by treatment received. All summaries will be derived based on available data. No imputation will be performed for missing values.

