1. INTRODUCTION

This document outlines the statistical methods to be implemented during the analyses of data collected within the scope of Helixmith Co., Ltd. (formerly ViroMed Co., Ltd.) Protocol VMNHU-003/I [A Phase III, Double-Blind, Randomized, Placebo-Controlled, Multicenter Study to Assess the Safety and Efficacy of VM202 to Treat Chronic Nonhealing Foot Ulcers in Diabetic Patients with Concomitant Peripheral Arterial Disease (PAD)]. The purpose of this plan is to provide specific guidelines from which the analysis will proceed. Any deviations from these guidelines will be documented in the clinical study report.

Study enrollment commenced under Protocol VMNHU-003/C. There were 7 subjects enrolled under protocol version C, 5 enrolled under version E, 16 enrolled under version F, and 16 enrolled under version G; no subjects were enrolled under protocol version D, H or I.

Protocol VMNHU-003/E introduced the following changes to exclusion criteria in VMNHU-003/C:

- The study ulcer decreased by 50% or more at baseline from Screening (as assessed by comparison of post-debridement photos taken at Screening and Day 0); previously only ulcers that increased by 50% or more at baseline from Screening were excluded.
- Target ulcer located on an active (hot) Charcot foot; previously any Charcot foot was excluded.
- Body mass index (BMI) > 45 kg/m² at Screening; previously BMI > 35 kg/m² was excluded.
- All steroids except inhaled or ocular steroids; previously only high dose steroids were excluded.

Since these changes to the exclusion criteria were not expected to have a meaningful influence in favor of VM202 on the efficacy and safety parameters, no inferential analyses to account for the protocol version will be conducted. Descriptive summaries of the primary efficacy endpoint and overall adverse event rates will be produced for the subjects enrolled under different versions of the protocol.

Protocol VMNHU-003/F submitted with SAP revision C introduced the following changes to the inclusion criteria:

- the upper age limit for study participants will be raised to 80 years;
- addition of ABI > 1.4 (indicative of non-compressible vessels at the ankle) as a qualifying criterion for documented PAD;
- revision of 1 criterion for documented PAD to: history of lower extremity peripheral artery disease with previous related intervention in a leg.

Protocol VMNHU-003/G introduced the following changes to the exclusion criteria:

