9.5. Safety Analyses

No formal statistical testing will be conducted for the safety analyses. The following sections summarize the descriptive analysis presented for these safety endpoints. All subjects in the safety population will be included in these analyses, with subjects grouped by the actual treatment received. All summaries will be derived based on available data at scheduled visits; safety data at unscheduled visits will only be included in data listings. No imputation will be performed for missing values.

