10. INTERIM ANALYSIS

Due to the early stopping of the study, the protocol-specified interim analysis will not be conducted.

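### SAP 9.5.3 guarantees no SAE-specific count by arm: the SAE summary is produced only if a preferred term repeats

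*SAP*

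**What the plan says.** SAP 9.5.3 makes one SAE output unconditional: "A listing of treatment-emergent SAEs (if any) will be provided". The table has a condition attached: "if more than one occurs within any given preferred term, a summary of treatment-emergent SAEs by SOC and preferred term will be created".

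The same section lists six adverse event summaries that are always produced: an overall summary, and summaries by SOC and preferred term, by injection number, by protocol version, by maximum severity and by relationship to treatment. The first is described as "Overall summary of TEAEs, which includes the subject incidence of TEAEs and total number of unique TEAEs from each of the following AE summaries".

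SAP 9.5 sets how safety results are presented: "All subjects in the safety population will be included in these analyses, with subjects grouped by the actual treatment received". Any SAE table, if made, would therefore be by arm. Protocol 6.3.3 states the purpose: "Safety analyses in this study will evaluate the safety profile of VM202, as compared with control". Safety is also one of the two analysis objectives in SAP section 2. Protocol 6.3.3 and SAP 9.5 both rule out formal testing of safety.

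**The concern.** With no formal testing, descriptive counts by arm are the whole of the safety comparison, and the proportion of subjects with an SAE is among the first figures a reader looks for. Under this rule, whether that figure appears depends on whether two events were coded to the same term. Two SAEs with one term in a single subject would produce the table. Eight subjects with eight different SAEs, all in one arm, would not.

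The small trial makes this a practical matter. SAP section 1 gives enrolment as "7 subjects enrolled under protocol version C, 5 enrolled under version E, 16 enrolled under version F, and 16 enrolled under version G", and SAP section 10 confirms the early end: "Due to the early stopping of the study, the protocol-specified interim analysis will not be conducted". In a trial of this size, SAEs with no repeated term are plausible. The documents give no expected SAE rate, so this is a judgement, not a finding.

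**Working it through.** The plan states no figure for this rule, so there is none to reproduce. The check has two parts.

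**1. Does any other output supply an SAE count by arm?**

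- The summaries by SOC and preferred term, injection number, protocol version and relationship count every TEAE, serious or not, with no split by seriousness.
- The maximum-severity summary is no substitute. Protocol 5.2.2 grades intensity by interference with routine activity; Protocol 5.1 defines seriousness by outcomes such as death, hospitalization or permanent impairment.
- The overall summary takes its rows from the other adverse event summaries. It does not name SAEs. It could carry an SAE row only if the SAE summary counts as one of those others, and then only when that summary has been triggered.
- SAP section 1 promises overall adverse event rates by protocol version, not SAE rates.
- The tables in SAP 8.5 go to the DSMB and are not promised as study-report outputs.

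So nothing in the plan secures the count when the trigger is not met.

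**2. How often would the trigger not be met?**

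Inputs: the number of SAEs, k, and the number of preferred terms they can fall into, m. Neither is in the documents, so both are assumptions. With m equally likely terms and events coded independently,

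P(no repeated term) = (m/m) × ((m−1)/m) × … × ((m−k+1)/m).

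Worked example, m = 20, k = 4: (19 × 18 × 17)/20³ = 5,814/8,000 = 0.727.
Worked example, m = 40, k = 6: (39 × 38 × 37 × 36 × 35)/40⁵ = 0.675.

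| SAEs (k) | m = 20 | m = 40 | m = 50 | m = 100 |
|---|---|---|---|---|
| 4 | 73% | 86% | 88% | 94% |
| 6 | 44% | 67% | 73% | 86% |
| 8 | 20% | 47% | 55% | 75% |
| 10 | 7% | 29% | 38% | 63% |

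For any fixed m, an even spread gives the highest chance of no repeat; clustering on common terms lowers every entry. More terms raise it.

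**What could go untabulated as SAEs.** Enrolment is 7 + 5 + 16 + 16 = 44. Subjects "will be randomized in a 2:1 ratio to one of two treatment groups", and 44 × 2/3 = 29.3, so I assume 29 on VM202 and 15 on placebo; the actual split is not given. I also assume one SAE per subject. Two-sided Fisher p-values serve here only to gauge the imbalance:

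- 6/29 (20.7%) against 0/15: p = 0.080
- 8/29 (27.6%) against 0/15: p = 0.037
- 0/29 against 4/15 (26.7%): p = 0.010

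Each pattern would leave the SAE table unmade if all its terms differed.

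**The case against.** The strongest reply is that the events are not hidden. Every treatment-emergent SAE is also a TEAE, so it is counted in the by-arm TEAE tables. A reader might infer from the rule that scattered SAEs would appear only in a listing, or that several different serious infections within one SOC would go unseen. The documents do not support this: the SOC and preferred term table would show such a cluster by arm. What it would not show is that the events were serious.

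Second, the table is most likely to be missing when SAEs are few and the listing is short enough to read in full. With 10 SAEs and 20 to 40 terms it is missing only 7–29% of the time, and once triggered it covers all treatment-emergent SAEs. This stands, with two limits: the SAP does not say that the listing shows treatment, and a short listing still gives no percentage.

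Third, the even spread is the least favourable case for the plan, and extreme one-sided patterns are uncommon. If the arms have equal risk, the chance that all eight of eight SAEs fall on VM202 is about (2/3)⁸ = 4%. Both points stand. They limit how much weight the figures can carry but do not change the rule. An arm difference caused by treatment, which is what the comparison exists to show, is not governed by that 4%.

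Fourth, the overall summary could be read as including an SAE row. That is reasonable when the SAE summary has been made; it does not cover the case where it has not.

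A reader might also infer that deaths and discontinuations due to adverse events are deliberately left out. The SAP promises no separate count by arm for either, but SAP 9.2 summarises early termination and Protocol 3.5.2 requires reasons to be recorded. That is a lesser matter and adds no weight here.

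**Conclusion.** The concern holds in a limited form. Followed as written, SAP 9.5.3 can leave the study report with no SAE-specific count or percentage by arm, although its safety analyses are meant to compare VM202 with control. This rests on the wording alone and needs no assumption about SAE numbers.

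The likelihood does rest on assumptions. The 20 to 40 equally likely terms are illustrative and come from no document; clustering lowers the percentages, and 50 or 100 terms would raise them.

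It would go too far to conclude that the trial cannot report SAEs by arm or that a safety signal would be concealed. The events remain in the TEAE tables and the listing, and a programmer may add the row unprompted; the plan simply does not require it. Severity is minor to moderate: safety is descriptive, and no primary result, error rate or data collection is affected.

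**What to change.** Replace the conditional sentence in SAP 9.5.3 with an unconditional one to this effect: the number and percentage of subjects with at least one treatment-emergent SAE, and the number of such events, are always tabulated by actual treatment received, overall and by SOC and preferred term. Add an SAE row to the overall TEAE summary, and state that the SAE listing shows treatment received. Rows for deaths and for adverse events leading to discontinuation are an optional addition.

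The cost is one sentence and one small table. Protocol 5.2 already requires seriousness to be recorded for every adverse event, so no new data are needed.
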